### **6.2.3.2 Repeat Treatment and Follow-up**

Repeat treatment is offered to treatment group subjects who complete the Month 12 visit. If accepted, they will return for repeat treatment within 14 days after the Month 12 follow-up visit.

The order in which the infraorbital hollows are treated will be the same as that for initial treatment. Female subjects of childbearing potential will take a urine pregnancy test; if the test is positive, the subject will not receive repeat treatment and will be exited from the study. The repeat treatment visits and procedures are identical to those for the initial treatment.

Subjects will be followed for 1 month after repeat treatment and will exit the study.

The procedures and evaluations to be performed during repeat treatment and follow-up are listed by visit in [Table 3](#).

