## 6.5 Early Discontinuation of Subjects

Each subject reserves the right to withdraw from the study at any time without jeopardy to his/her future medical care. All follow-up procedures scheduled to be performed at the final site visit should be performed at the subject's last site visit. Subjects may also be administratively withdrawn if they do not return for follow-up visits. For any subject who withdraws from the study, the date and reason for withdrawal will be recorded on the eCRF. If a treatment-related AE is ongoing at the time of withdrawal, the TI will attempt to follow the subject until the AE has been resolved or follow-up is no longer possible. The TI shall ask for the subject's permission to follow his/her status/condition outside the study.

Randomized subjects who withdraw before treatment will not be replaced by another subject. The subject number and associated randomization number of the withdrawn subject should not be reassigned to a different subject.

If a subject fails to return for 1 or more scheduled study visits, the TI (or designee) will attempt to contact the subject to determine and document the reason the subject has failed to return and to encourage compliance with the study visit schedule.

At regular intervals, the TI (or designee) will record on the eCRF the reasons for which any subjects are discontinued from the study, including subjects who signed the ICF but do not proceed to randomization.

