## 8. Statistical Procedures

A separate statistical analysis plan will be prepared to provide specifications for all analyses. The plan will be finalized and approved prior to clinical database lock. One database lock is planned after all subjects exit the study.

Descriptive statistics will be presented for key outcome measures. Categorical variables will be summarized with frequency and relative frequency. Continuous variables will be summarized by number of subjects, mean, median, standard deviation, 1st and 3rd quartiles, minimum, and maximum. Where appropriate, 2-sided 95% CIs for population mean, or population proportion, will be provided as part of the descriptive summary.

Every attempt will be made to collect complete data and limit the occurrence of missing data. Imputation of missing data may be used for sensitivity analysis of the primary effectiveness endpoint. Deviations from the analyses planned in the statistical plan will be documented in the clinical study report.

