## **11. Adverse Events**

Throughout the course of the study, all AEs will be monitored and reported on an AE eCRF, including seriousness, severity, action taken and relationship to study treatment. If AEs occur, the first concern will be the safety of the study participants.

Although the risk of developing a serious complication is small, the TI and the research staff will monitor each subject closely, and, if a complication occurs, they will use their medical

judgment to do whatever is necessary to treat the problem. If subjects have any ongoing treatment-related SAEs at the time of the final visit, they must continue to be followed up until resolution of these events or the subject condition is considered stable by the TI. After the final visit, the subject will resume receiving the standard medical care according to the standard care of the clinic.

Typical or expected AEs or risks include bruising, swelling, redness, tenderness, and/or itching at the treatment site. Additional information about the possible side effects is available in the IDFU for VOLBELLA XC.

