### 11.3 Procedures for Reporting an AE or ADE

All AEs or ADEs occurring during the study period (beginning with signing ICF) are to be recorded on the appropriate eCRF by the TI. Any AE that is ongoing at the exit visit must be followed up as appropriate.

The TI will report AESI interest to Allergan within 24 hours of awareness of the event by completing an AE eCRF and notifying Allergan study management personnel and the Medical Safety Physician by fax or email. Allergan will notify FDA of any AESI within 10 days of Allergan’s awareness of the event.

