5.1.1.6.1 Adverse Events

An AE will be considered a TEAE if:

- The AE began on or after the date of the first dose of study intervention; or
- The AE was present before the date of the first dose of study intervention, but increased in severity or became serious on or after the date of the first dose of study intervention; or
- For the control group, AE began on or after the date of randomization; or
- For the control group and prior to the initial treatment, if AE was present before randomization, but increases in severity on or after randomization date, the AE is considered as TEAE.

An AE will be considered a treatment-emergent SAE if it is a TEAE that additionally meets any SAE criteria.

AEs and encompassing abnormalities, reported as occurring after the Screening Visit, will be coded using MedDRA version 20.1 or newer. A listing for all TEAEs in the treatment and control groups will be presented. AEs that occur before initial treatment for the treatment group and randomization for the control group will be listed. Additionally, unique participants reporting AEs as well as the number of events in the following AE categories will be summarized for treatment participants, control participants after optional treatment, and all treated participants as follows:

Table 5-7 AE Summaries

Endpoint	Description	Timing	Methodology
Overall summary	Overall summary only for the following categories: 
 • TEAEs • Treatment-related TEAEs • Treatment-related TEAEs at injection site • Treatment-related TEAEs not at injection site • SAEs • Treatment-related SAEs • Treatment-related SAEs at injection site • Treatment-related SAEs not at injection site • Discontinued due to TEAE • Deaths 	
 • CP • TP (12-Month) • Repeat Treatment Period • TP (9-Month) 	Categorical counts, Event descriptive
TEAEs	
 • Overall Summary and by SOC, PT 		Categorical counts, Event descriptive
TEAEs	
 • Overall summary and by SOC, PT and severity 		Categorical counts, Event descriptive
Treatment-related TEAEs	
 • Overall summary and by SOC, PT 		Categorical counts, Event descriptive
	
 • Overall summary and by SOC, PT and severity 		
	
 • Summary by duration, time to onset, severity, causality, treatment required, and outcome 		

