Note: SOCs and PTs will be sorted in descending frequency in the treatment group, then control group. AEs for control group before and after optional treatment are summarized separately.

For participants who receive repeat treatment, their AEs reported during the first months in the initial treatment period will be summarized and presented in parallel with AEs reported during the repeat treatment period.

Overall summary by severity for TEAEs and treatment-related TEAEs will also be summarized by the primary injection instrument used (needle vs cannula).

If more than 1 AE is coded to the same PT for the same participant, the participant will be counted only once for that PT using the most severe and most related occurrence for the summarizations by severity and by relationship to study intervention.

Time to onset for TEAEs will be computed as

$$\text{AE start date} - \text{reference date} + 1,$$

where the reference date is initial treatment date for TEAEs occurring on or after initial treatment but before touch-up treatment and the reference date is touch-up treatment date for TEAEs occurring on or after touch-up treatment but before repeat treatment.

Duration for TEAEs will be computed as AE end date – AE start date + 1. If AE end date is not available, duration for TEAEs will not be computed.

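### Does leaving TEAEs without an end date out of the duration calculation distort the safety summary after repeat treatment?

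*SAP*

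**What the plan says.** SAP section 5.1.1.6.1 computes TEAE duration from the start and end dates, with one exception: "If AE end date is not available, duration for TEAEs will not be computed". Table 5-7 in the same section includes, for treatment-related TEAEs, a "Summary by duration, time to onset, severity, causality, treatment required, and outcome". The timings given for that table include the Repeat Treatment Period, and the methodology is counts of participants and events.

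That period is short. Protocol section 6.2.3.2 states: "Subjects will be followed for 1 month after repeat treatment and will exit the study". SAP Table 5-1 ends it at study exit. For participants who are retreated, the SAP also plans a side-by-side display, in which "AEs reported during the first months in the initial treatment period will be summarized and presented in parallel" with those of the repeat period.

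The protocol provides for follow-up beyond exit. Section 11.3 says "Any AE that is ongoing at the exit visit must be followed up as appropriate". For related serious events still open at the final visit, section 11 says "they must continue to be followed up until resolution of these events or the subject condition is considered stable by the TI". For related events open at withdrawal, section 6.5 says "the TI will attempt to follow the subject until the AE has been resolved or follow-up is no longer possible". Section 8 adds: "One database lock is planned after all subjects exit the study".

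SAP section 6.3.2 imputes partial end dates only, capped at study exit when both fall in the same month or year. SAP section 4 leaves table layouts to a separate document.

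**The concern.** For a given onset, the longer an event lasts, the likelier it is to be open at exit. If only events with an end date get a duration, the summary describes the events that resolved in time and understates how long reactions last. A 12-month period hardly suffers, but a 1-month period can. The same true durations could then look shorter after repeat treatment than after initial treatment, which would flatter the safety of retreatment.

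The SAP text neither censors open events nor says how they are shown beside the durations. It also does not say whether end dates learned after exit are used.

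**Working it through.** The plan states no figure for event duration or for the share of events without an end date, so there is nothing to reproduce. The question is how large the effect could be under stated assumptions.

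**Inputs.** Follow-up after repeat treatment F = 30 days (Protocol section 6.2.3.2, taking 1 month as 30 days). Assumed: the duration distribution, its mean m, the onset time, and the share r of missing end dates obtained after exit.

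**Exponential durations, onset on the treatment day.** Let e = exp(−F/m).

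- Share with no duration = (1 − r) × e.
- Mean among events resolved by day 30: μ = m − F × e/(1 − e).
- Mean among all events with an end date = [(1 − e) × μ + r × e × (F + m)] / [(1 − e) + r × e].

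For m = 14 and r = 0: e = exp(−30/14) = 0.1173, and μ = 14 − 30 × 0.1173/0.8827 = 10.0 days. For r = 0.8 the share is 0.2 × 0.1173 = 2.3%, and the mean is (0.8827 × 10.01 + 0.8 × 0.1173 × 44)/(0.8827 + 0.0938) = 13.3 days.

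| True mean (days) | No duration, r = 0 | Mean seen | No duration, r = 0.5 | Mean seen | No duration, r = 0.8 | Mean seen |
|---|---|---|---|---|---|---|
| 7 | 1.4% | 6.6 | 0.7% | 6.8 | 0.3% | 6.9 |
| 10 | 5.0% | 8.4 | 2.5% | 9.2 | 1.0% | 9.7 |
| 14 | 11.7% | 10.0 | 5.9% | 12.1 | 2.3% | 13.3 |
| 30 | 36.8% | 12.5 | 18.4% | 23.2 | 7.4% | 27.6 |

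With r = 0 the loss reaches 5% at m = 30/ln 20 = 10.0 days and 10% at m = 30/ln 10 = 13.0 days.

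**Tighter durations.** Lognormal, log-SD s = 0.5, onset on the treatment day, r = 0. The share with no duration is 1 − Φ[(ln 30 − ln m + s²/2)/s].

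- m = 10: 1 − Φ(2.447) = 0.7%.
- m = 14: 1 − Φ(1.774) = 3.8%.
- m = 21: 1 − Φ(0.963) = 16.8%.

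**Later onset.** Exponential, onset even over the first 14 days, r = 0. The share is (m/14) × [exp(−16/m) − exp(−30/m)], which gives 4.4% at m = 7 and 20.2% at m = 14.

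**12-month period for comparison.** Exponential, early onset, with the 20% dropout of Protocol section 5.1 spread evenly over 365 days (timing assumed). The share is 0.8 × exp(−365/m) + 0.2 × (m/365) × [1 − exp(−365/m)], which gives 0.8% at m = 14.

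**Reading.** The direction is certain for a given onset. At a mean of 14 days the loss runs from 2.3% to 20.2% across these cases, and the documents do not say which applies. No threshold for the mean duration can be drawn from them.

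**What the rule removes.** It withholds a computed duration; it does not say that the event leaves the table or its denominator. Table 5-7 is a table of counts, in which an event without a duration can be shown as missing or ongoing. The SAP names no mean duration for TEAEs, so the mean columns above illustrate the direction of the effect only. Outcome stands in the same Table 5-7 item as duration, and section 5.1.1.6.1 also calls for a listing of all TEAEs. Unresolved events therefore remain visible.

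**The case for a change.** The strongest case for a change is that the bias is built in and not a matter of chance, that it is largest where follow-up is shortest, and that the cure is cheap: one table row per period for ongoing events and one sentence on dates obtained after exit. Longer events are plausible, since Protocol section 11.1.1 lists nodules, discoloration, granulomas and delayed lumps or swelling among known risks, some of them described as rare. At a mean of 14 days the exponential case loses 11.7% in the repeat period against 0.8% over 12 months. SAP Table 6-4 also marks a wholly missing date as imputable, which fits poorly with the rule on durations, and no target date is given for AE end dates.

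Most of this stands as description, but less of it stands as a reason to amend the SAP:

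- An ongoing row would largely repeat what the outcome summary shows, and the separate table specification, not available here, may already contain one.
- On its plain reading the duration formula uses whatever end date is recorded, with no cap at exit. The cap in section 6.3.2 applies only to imputed partial dates.
- The side-by-side display of initial and repeat treatment is not said to include durations.
- Injection site responses have their own duration analysis from the 30-day diary, including after repeat treatment (SAP Table 5-8).
- Table 6-4 is a general convention. Sections 5.1.1.6.1 and 6.3.2 are specific to AE durations and end dates, and an analyst would follow them.

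**Conclusion.** No change to the plan is needed. Durations among resolved events will tend to be short in the 1-month repeat period. The loss is about 1% if events last about a week and begin on the treatment day. At a mean of 14 days it is 2.3% to 20.2%, depending on the assumed spread, onset and recovery of end dates after exit. All of these durations are assumptions. The effect is confined to one descriptive safety summary in an optional treatment period. Incidence, severity, outcome, listings, every test and every effectiveness result are untouched. What the SAP leaves open is display detail that analysts would settle sensibly when they lay out the table: count events with no end date beside the durations, and use the end dates on record at database lock.

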5.1.1.7 ISR

ISRs recorded in participant diaries after each treatment (initial, touch-up, and repeat) will be summarized during that treatment by pre-defined symptoms.

Table 5-8 **ISR Analyses**

Endpoint	Description	Timing	Methodology
ISR severity	Maximum reported severity.	Initial, Touch-up, Repeat	Categorical counts
ISR duration	Duration from first instance of the ISR to the last instance of the ISR within the treatment period, where last instance means no further symptoms until the end of the 30-day diary collection period	Initial, Touch-up, Repeat	Categorical counts

ISR severity and ISR durations analyses described in Table 5-8 will also be summarized by the primary injection instrument used (Needle vs Cannula).

If a participant reported more than one “Other” ISR, the participant will be counted once in the summary for that treatment. If the incidence of any particular category of “Other” ISRs is greater than 5%, then the severity and duration analyses described in Table 5-8 will be performed for that specific category of the “Other” ISR.

[figure not shown]
[REDACTED]

[REDACTED]

[REDACTED]

[REDACTED]

[REDACTED]

5.1.1.9 Vital Signs

Vital signs will be provided in a listing.

5.1.1.10 Pregnancy Test Analyses

Urine pregnancy test is performed (for female participants of childbearing potential) at screening, randomization, prior to every treatment (initial, touch-up, and repeat), and study exit. Participants with a positive result will be presented in a listing.

5.1.1.11 Interim Analyses

No interim analysis is planned for this study.

5.1.2 Determination of Sample Size

Table 5-10 **Sample Size Assumptions**

Parameter	Assumption/Estimate
Primary endpoint	
Risk difference	
A	
Sides	
Power	
N per group	
N total	

5.2 **Changes in the Conduct of the Study or Planned Analyses**

The primary analysis was changed from as-observed to multiple imputation so that all participants in the mITT will be used for statistical inference.

5.2.1 **Changes in the Conduct of the Study**

Not applicable.

5.2.2 **Changes to Analyses Prior to Database Lock**

Not applicable.

6. Data Handling and Analysis Conventions

6.1 Study Treatment Conventions

6.1.1 Analysis Days

Treatment day for effectiveness, ISR, and AE are defined as follows:

Table 6-1 Analysis Day Definitions

Term	Description
Effectiveness: Effectiveness Day	
JUVÉDERM VOLBELLA XC and control (only the control participants receiving optional treatment): Relative to the last treatment date (either the initial treatment, if no touch-up is performed, or the touch-up treatment, repeat treatment)
 
 • Effectiveness Day = analysis date - last treatment start date + 1 ○ Effectiveness Day 1 = last treatment start date 
Control (before receiving optional treatment): Relative to the randomization date
 
 • Effectiveness Day = analysis date - randomization date +1 • Effectiveness Day 1 = randomization date
Safety (including AE and ISR): Safety Day	
JUVÉDERM VOLBELLA XC and treated control (only the control participants receiving optional treatment): Relative to treatment date (initial and touch-up)
 
Safety Day = analysis date - treatment date + 1 Safety Day 1 = treatment date
 
Control (before receiving optional treatment): Relative to the randomization date
 
 • Safety Day = analysis date - randomization date +1 • Safety Day 1 = randomization date 
JUVÉDERM VOLBELLA XC Only: Relative to the repeat treatment date (after repeat treatment)
 
 • Safety Day = analysis date - repeat treatment date + 1 • Safety Day 1 = repeat treatment date

6.2 Analysis Visit Windows

All scheduled and unscheduled visits with complete dates will be assigned visit windows and used for analysis. However, if a scheduled visit with incomplete date is available with no other visits with complete date during the visit window, then the visit with incomplete date may be used for analysis and the nominal visit will be used as the visit window (eg, if the only assessment collected for Month 3 visit window is on a Month 3 eCRF with incomplete date, then those data will be used for the Month 3 assessments).

If there are multiple visits occurring within a single visit window with relevant data, the visit closest to the target day will be used in the analysis of the corresponding visit windows. If 2 visits are equal distance to the target day and are the same type of visit, then the later visit will be used.

Analysis visit windows for effectiveness endpoints and safety are defined as follows.

6.2.1 Effectiveness

The analysis visit windows for effectiveness endpoints are defined as follows:

Table 6-2 Effectiveness Analysis Visit Definitions for Treatment Group and Control Group during Treatment Period

Scheduled Visit for Effectiveness Measure	
Screening ^a	
Touch-up Treatment ^b	
Last Treatment ^c	
Month 1	
Month 3	
Month 6	
Month 9	
Month 12	
Repeat Treatment ^d	
Month 1 Repeat	

^a Participants may have screening visits

^b Not all participants will receive touch-up treatment

^c Initial treatment if touch-up is not performed, otherwise touch-up treatment

^d Not all participants will receive repeat treatment

Table 6-3 Effectiveness Analysis Visit Definitions for Control Group during Control Period

Scheduled Visit	
Randomization Day	
Month 1	
Month 3	

6.2.2 Safety

No analysis visit windows are required for TEAEs and ISRs. Nominal visit will be used for summarizing Snellen visual acuity, ocular motility, and Tyndall effect.

6.3 Missing/Incomplete Date Conventions

Dates may be imputed with year, month, and day values under certain scenarios:

Table 6-4 Imputation Scenarios

Scenario	Complete			Imputable
	Year	Month	Day	
1	Yes	Yes	Yes	Complete
2	Yes	Yes	—	Yes
3	Yes	—	Yes	No ^a
4	Yes	—	—	Yes
5	—	Yes	Yes	No ^a
6	—	Yes	—	No ^a
7	—	—	Yes	No ^a
8	—	—	—	Yes

^a Not allowed per database design.

Dates will be imputed initially toward a specified target date for imputable scenarios 2, 4, and 8, and adjusted against the latest reasonable dates. The initial imputed date is determined by the following algorithm:

Table 6-5 Initial Imputed Date Algorithm

Available Year (YYYY)	Available Month (MM)			
	Missing	< Target Month	= Target Month	> Target Month
Missing	Target Date	—		
< Target Year	YYYY-12-31	YYYY-MM-LD		
= Target Year	Target Date	YYYY-MM-LD	Target Date	YYYY-MM-01
> Target Year	YYYY-01-01	YYYY-MM-01		

LD = last day of the month; MM = available start date month; YYYY = available start date year.

6.3.1 Missing/Incomplete AE Start Date

Imputation of dates with missing day and/or month is only applied to TEAEs. If adequate information is available, no imputation is needed. TEAE start dates with missing day or month will be imputed as following:

- If day and month are missing but year is available, then the imputed day and month will be 01 Jan or the initial treatment date if they have the same year, whichever is later (because TEAE onset is not expected prior to administration of study treatment)
- If day is missing but the month and year are available, then the imputed day will be the first day of the month or the initial injection date if they have the same month and year, whichever is later.

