5.1.1.1 Common Conventions

5.1.1.1.1 Analysis Periods

- Participants will receive treatment at the outset of the study (treatment group) or have treatment delayed until Month 3 (control group). The delayed treatment for control group is optional and referred to as “Optional Treatment”.
- Participants in the treatment group may receive optional touch-up treatment at Day 30 or optional repeat treatment at the completion of Month 12.
- Participants in the control group may receive optional touch-up treatment at Day 30 after optional treatment.
- Analysis periods are defined in [Table 5-1](#) below.

Table 5-1 Analysis period definition

Randomization Group	Period	Treatment Group Label	Start Date	End Date
Treatment	CP	VOLBELLA	Initial treatment date	The date of effective assessment for Month 3. 
 • If multiple assessments fall into Month 3 window, the date of the assessment included in the Month 3 analysis will be used as end date. • For participants who exit before Month 3, the end date is study exit date. • For participants with missing assessment at Month 3, the target day for Month 3 (Day 91) will be the end date.
	TP (12-Month)	VOLBELLA	Initial treatment date	Study exit date or date prior to repeat treatment, whichever is earlier
	Repeat Treatment Period	VOLBELLA	Repeat treatment date	Study exit date
Control	CP	Control	Randomization date	For participants who do not receive optional treatment: 
 • If multiple assessments fall into Month 3 window, the date of the assessment included in the Month 3 analysis will be used as end date. • For participants who exit before Month 3, the end date is study exit date. • For participants with missing assessment at Month 3, the target day for Month 3 (Day 91) will be the end date. For participants who receive optional treatment: 
 • The day before optional treatment
	TP (9-Month)	VOLBELLA Post-Control	Optional initial treatment date	Study exit date

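### SAP 6.3.1 has no randomization-date floor for partial AE start dates in controls, so some control-period TEAEs can be misdated

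*SAP*

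**What the plan says.** SAP 6.3.1 sets the scope: "Imputation of dates with missing day and/or month is only applied to TEAEs". With only the year known, "then the imputed day and month will be 01 Jan or the initial treatment date if they have the same year", and the later of the two is taken. With month and year known, "the imputed day will be the first day of the month or the initial injection date" is used, again the later, if month and year agree. The stated reason is "because TEAE onset is not expected prior to administration of study treatment". One exemption is given: "If adequate information is available, no imputation is needed". Randomization is not mentioned.

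SAP 5.1.1.6.1 counts control TEAEs from a different origin: "For the control group, AE began on or after the date of randomization". Table 5-1 in SAP 5.1.1.1.1 starts the control group's Control Period (CP) at randomization. For those who take optional treatment the CP ends on "The day before optional treatment", and TP (9-Month) starts on the "Optional initial treatment date". The note to Table 5-7 requires control AEs before and after optional treatment to be summarized separately.

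**The concern.** The reason given for the floor holds for the treatment group, whose TEAEs start with the first injection. It contradicts the SAP's own TEAE definition for controls, who can have a TEAE throughout the no-treatment phase. A programmer who follows 6.3.1 literally could produce two kinds of wrong date for a control-period event:

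- **Before randomization.** The first of the month, or 1 January, can precede the start of the CP.
- **At optional treatment.** If the control group's initial treatment is taken to be the optional one, an event whose known month or year matches it is dated to the injection and falls in TP (9-Month).

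The CP is the only randomized safety comparison in the study. An untreated-period event that moves across the boundary leaves the control column and appears as an event after device use.

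**Working it through.** The plan gives no figure for this, so the check applies the two bullets of 6.3.1 literally to control-period AEs.

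**Inputs**
- Controls: 140 randomized at 3:1 (Protocol 4.5 and 5.1), so 140 × 1/4 = 35. One participant is 1/35 = 2.9 percentage points of a control incidence.
- Optional treatment: at Month 3 (target Day 91, Table 5-1) or up to 2 weeks later (Protocol 6.2.4.2), hence Day 91, 98 or 105.
- Decliners complete the study after the Month 3 visit (Protocol 6.2.4.1). Day 91 is used.
- Assumptions: randomization equally likely on each of 365 days; onset uniform from randomization to the day before optional treatment (to Day 91 for decliners); no clause spares the record.

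**Rule**
- Day missing: imputed start = later of the 1st of the month and the treatment date, if month and year match.
- Year only: imputed start = later of 1 January and the treatment date, if the year matches.

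**Treated controls, with optional treatment counted as initial treatment**

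| Treatment day | Onset days enumerated | Missing | Stays in CP | Moved to treatment | Before randomization |
|---|---|---|---|---|---|
| 91 | 365 × 90 = 32,850 | day | 67.3% | 16.4% | 16.4% |
| 98 | 365 × 97 = 35,405 | day | 69.6% | 15.2% | 15.2% |
| 105 | 365 × 104 = 37,960 | day | 71.7% | 14.2% | 14.2% |
| 91 | 32,850 | day and month | 0% | 87.5% | 12.5% |
| 98 | 35,405 | day and month | 0% | 86.6% | 13.4% |
| 105 | 37,960 | day and month | 0% | 85.6% | 14.4% |

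**Decliners** (365 × 91 = 33,215 onset days): 16.2% fall before randomization with the day missing, 87.4% with only the year known.

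**Narrower reading**, where initial treatment means the treatment group's injection only: nothing moves to optional treatment. In treated controls 14-16% (day missing) and 86-88% (year only) then fall before randomization.

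**Example.** Randomized 20 March; optional treatment 18 June (Day 91).
- Onset 25 March, recorded as March: imputed to 1 March, 19 days before randomization.
- AE of 5-10 June, start recorded as June, end known. On the broader reading the start becomes 18 June, in TP (9-Month). By the SAP formula (end − start + 1) the duration is 10 − 18 + 1 = −7 days; the true value is 10 − 5 + 1 = 6.

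**The case against.** Several limits on the point stand.

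- **Clauses that may spare records.** The adequate-information exemption could protect an AE whose end date already places it before treatment, as in the June example. The parent section, SAP 6.3, also says that imputed dates are adjusted against the latest reasonable dates, which could act as a cap. Neither is defined for AE start dates, so the fair criticism is vagueness rather than the absence of any safeguard.
- **The move to optional treatment depends on a reading.** Table 5-1 uses a separate label for the control group's injection. SAP 5.1.1.6.1, however, speaks of controls prior to the initial treatment, so the broader reading is natural but not certain.
- **Duration and time to onset.** A reader might infer that negative durations, or onset times of 1 day, will appear widely. Table 5-7 tabulates these only for treatment-related TEAEs, and a control-period AE in an uninjected participant is unlikely to be judged related (Protocol 11.1.9). The main route is a missing relationship imputed as related under Table 6-6, a second rare condition on top of a partial date.
- **Loss from the tables.** A reader might infer that an event dated before randomization drops out of the control summary. The documents do not say so. 6.3.1 acts on events already classed as TEAEs, and such an event still precedes optional treatment. It is lost only if the Table 5-1 start date is applied as a hard filter. The pre-randomization shares are therefore wrong dates, not demonstrated wrong counts.
- **Denominator.** Controls are seen at Months 1 and 3, so year-only dates should be rare.

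**Conclusion.** The contradiction is real: the stated reason for the 6.3.1 floor is false for controls under the SAP's own TEAE and period definitions. Pre-randomization dating follows from the literal rule on either reading. Movement into TP (9-Month), against the separate before-and-after summaries, follows only if the optional injection counts as the initial treatment.

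The computed shares are of partially dated control-period AEs. They rest on uniform randomization and onset and on no clause sparing the record; they fall to zero if every record is spared. How many such AEs there will be is unknown and may be none. The effect is mainly on period assignment in descriptive safety tables for about 35 controls. TEAE status is not shown to change, and the primary effectiveness test is untouched. Minor severity, medium confidence.

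**What to change.** In SAP 6.3.1, for control participants:

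1. Replace the floor for a partial AE start date with the randomization date.
2. Use the optional treatment date as the floor only if the AE is recorded as starting on or after that treatment, or if the partial date fits both periods and nothing recorded (such as the AE end date) places onset before it. Flag the events in this second group.
3. Do not let an imputed start date exceed a known AE end date.

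In the example the starts become 20 March and 1 June, both in the CP, and the second duration is 10 − 1 + 1 = 10 days. No control AE is dated before randomization. The share moved to treatment depends on what is recorded: zero if every event can be placed before treatment, unchanged at 14-16% (day missing) or 86-88% (year only) if none can.

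The cost is a few SAP sentences and minor programming before database lock. The rule should not depend on the visit of first report, because the documents do not show that the eCRF captures it. The downside is that events that stay ambiguous are still attributed to the device period, which is why they need a flag.
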